1. INTRODUCTION

The purpose of this reporting and analysis plan (RAP) is to describe the analyses to be included in the Clinical Study Report for Protocol:

| Revision Chronology: | | |
|----------------------|-------------|-------------|
| 2016N290366_02 | 11-OCT-2017 | Amendment 2 |

2. SUMMARY OF KEY PROTOCOL INFORMATION

2.1. Changes to the Protocol Defined Statistical Analysis Plan

Bystander and Environmental Exposure Analyses will be reported in a separate report.

The Lung ELF Concentration population for analysis is renamed to BAL PK in order to keep it consistent with the other Phase I study (202031).

The All Participants Screened, Safety, Systemic Pharmacokinetic Concentration (PK), the BAL PK analysis populations are not defined separately for Part 1 and Part 2 as mentioned in the protocol.

For the data disclosure outputs regarding "Summary of Age Ranges", the Enrolled population is defined in this RAP.

[figure not shown]
The term "Subjects" is used to refer to the "Participants" in certain sections of this document including the TFLs.

[figure not shown]
2.2. Study Objective(s) and Endpoint(s)

| Objectives | | En | Endpoints | |
|------------|---|----|---|--|
| Pri | Primary Objectives | | Primary Endpoints | |
| • | To investigate the safety and tolerability of CCI15106-IP following single and repeat escalating doses in healthy participants and participants with moderate COPD. | • | Adverse events (AEs), clinical laboratory, electrocardiogram (ECG), telemetry, spirometry, and vital signs assessments. | |
| • | To determine systemic PK of CCI15106 following single and repeat escalating doses of CCI15106-IP in healthy participants and participants with moderate COPD. | • | Derived systemic PK parameters of CCI15106: Single dose: area under the curve (AUC) from time zero to the time of last quantifiable concentration (AUC[0-last]), concentration at maximum (Cmax), time of maximum concentration (tmax), AUC from time zero to infinity (AUC[0- ∞]) elimination half-life (t1/2), clearance (CL/F), as data permit. Repeat dose: AUC from time zero to end of dosing interval (AUC[0- τ]) (τ =12 hours [h] for twice daily dose regimen), Cmax, tmax, elimination half-life (t1/2) as data permit. | |
| • | To evaluate potential inhalation exposure of bystanders to airborne | • | Concentration of CCI15106 in plasma of bystanders 15- 20 minutes (min) after dosing (at predicted tmax) and | |

| Objectives | Endpoints |
|---|--|
| CCI15106 during self-administered dosing of participants. | amount of CCI15106 accumulated on filters fitted on bystander over 15 min after dosing. |
| To evaluate the distribution and persistence of airborne CCI15106 in room air post-dosing. | Amount of CC15106 in room air assessed by measuring amount of CCI15106 accumulated over 20 and 60 min intervals during and immediately post-dosing on filters fitted on stationary pumps placed in the room. |
| Secondary Objectives | Secondary Endpoints |
| To determine the concentration of CCI15106 in the lung of healthy participants and participants with moderate COPD following repeat dosing of CCI15106-IP. | Concentrations of CCI15106 in lung epithelial lining fluid (ELF) assessed by bronchoalveolar lavage (BAL). |
| To investigate the performance of the Monodose RS01 device for the administration of CCI15106-IP in healthy participants and participants with moderate COPD. | Device safety and performance parameters, including medical device incidents reporting, as well as systemic PK and lung CCI15106 concentrations. |
| Exploratory Objectives | Exploratory Endpoints |
| To assess dose proportionality of CCI15106-IP versus systemic PK parameters. | Comparisons of doses administered and systemic PK parameters of CCI15106: AUC(0-24) or AUC(0-τ) and Cmax. |
| To explore the relationship of drug exposure to safety and tolerability parameters after single and repeat escalating doses of CCI15106-IP in healthy participants and participants with moderate COPD. | The dose or plasma exposure parameters for CCI15106 and the relationship of these to safety and tolerability parameters, as data permit. |
| To extrapolate study outcomes to a realistic worst case real-life scenario of dosing multiple patients in a single room in a nursing home. | Comparison of the study room with a potential nursing home room, including room dimensions, patient density, ventilation (air change rates per hour). |

2.3. Study Design

2.4. Statistical Hypotheses

The primary objective of the study is to investigate the safety and tolerability of CCI15106-IP following single and repeat escalating doses in healthy participants and participants with moderate COPD. No statistical hypotheses will be tested.

3. PLANNED ANALYSES

3.1. Interim Analyses

No formal interim analyses are planned for this study. Safety and tolerability will be evaluated as described in Section 2.3. Systemic and, where available, lung PK may also be evaluated.

3.2. Final Analyses

Safety and PK analyses are the primary statistical analyses for this study.

Data will be listed and summarized according to GSK reporting standards, where applicable. All the displays will be split by part. Study population tables would be presented by cohort and a combined placebo (of all cohorts with the exception of Part 1, Cohort C (bystanders)). For Safety displays, listings will be sorted by dose, participant and time; summaries will be presented by dose and time for different parts of the study. Participants receiving placebo may be combined into one treatment group in the summaries within each part.

Descriptive summaries will include n, mean, standard deviation (SD), median, minimum, and maximum, geometric mean with associated 95% confidence interval (CI), and the between-participant coefficient of variation (%CVb) for continuous variables related to PK parameters, n and percent will be used as summary statistics for categorical variables.

Version 9.4 or higher of the SAS system will be used to analyse the data as well as to generate tables, figures, and listings.

4. ANALYSIS POPULATIONS

| Population | Definition / Criteria | Analyses Evaluated |
|--|--|---|
| All Participants Screened | Comprises of all participants who consent to participate in the clinical study. | Screen Failures |
| Enrolled | All participants who passed screening and entered the study. Note screening failures (who never passed screening even if rescreened) and participants screened but never enrolled into the study (Reserve, Not Used) are excluded from the Enrolled population as they did not enter the study. | Study Population |
| Safety | Comprises of all participants who receive at least one dose of study treatment during the study. This population will be based on the treatment the participant actually received. | SafetyStudy Population |
| Systemic Pharmacokinetic Concentration (PK) | Participants who receive at least one dose of study treatment and who undergo plasma PK sampling and have at least one post-dose concentration result. PK samples that may be affected by protocol deviations will be reviewed by the study team to determine whether | • PK |

| Population | Definition / Criteria | Analyses Evaluated | |
|--|---|--------------------|--|
| | or not the sample will be excluded. | | |
| BAL PK | Healthy participants who receive at least one dose of study treatment and who undergo BAL sampling and have post-dose lung ELF CCI15106 and urea concentration result. | • BAL | |
| | Lung ELF samples that may be affected by protocol deviations, will be reviewed by the study team to determine whether or not the sample will be excluded. | | |
| Bystander Safety | Participants who are present at least once in the room | Safety | |
| Population (Part 1, Cohort C) | with the participant receiving the dose. | Study Population | |
| Bystander PK Population (Part 1, Cohort C) | Participants who are present at least once in the room with the participant receiving the dose, undergo plasma PK sampling and have post-dose concentration result. | • PK | |
| | PK samples that may be affected by protocol deviations will be reviewed by the study team to determine whether or not the sample will be excluded. | | |

Refer to Appendix 11: List of Data Displays which details the population used for each display.

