8. PHARMACOKINETIC ANALYSES

8.1. Overview of Planned Pharmacokinetic Analyses

The PK analyses will be based on the "Systemic Pharmacokinetic Concentration" population for the plasma drug concentration data, and "BAL PK Population" for the lung ELF concentration data, unless otherwise specified.

Table 4 provides an overview of the planned analyses, with full details being presented in Appendix 11: List of Data Displays.

Table 4 Overview of Planned Pharmacokinetic Analyses

| Endpoints | | | Untr | ransfo | rmed | | | ormed | d | | | | | |
|------------------------------------|------|-------|-------|--------|-------------------|-----------------|------------|-------|----------------|-----------------|---|-----------------|------------|---|
| | Stat | s Ana | lysis | Sum | Summary | | Individual | | Stats Analysis | | | mary | Individual | |
| | T | F | L | T | F | F | L | Т | F | Ш | Т | F | F | L |
| Plasma Drug Concentrations | | | | Y | Y [1] [2] [3] [4] | Y [1] | Υ | | | | | Y [1] [2] | Y [1] | |
| Derived PK Parameters | Υ | | | Υ | | | Υ | Υ | Y [7] | Y [8] | | | | |
| Lung ELF CCI15106 Concentration | | | | Υ | Y [5] | Y [6] | Υ | | | | | | Y [1] | |

NOTES:

- T = Table, F = Figure, L = Listings, Y = Display generated.
- Stats Analysis = Represents TFL related to any formal statistical analyses (i.e. modelling) conducted.
- Summary = Represents TFL related to any summaries (i.e. descriptive statistics) of the observed raw data
- Individual = Represents FL related to any displays of individual participant observed raw data.
- 1. Linear and Semi-Log plots will be created on the same display.
- 2. Separate Mean (± SD) and Median plots will be generated, for the BD cohorts, overlay the day 1 and day 14 on same plot where possible.
- 3. Mean (± SD) and Median plots by cohorts a) to compare over the first 12hours for 60mg in HV (part 1) and COPD (part 2); b) to compare the 60mg SD (over 24h) HV vs COPD; c) to compare the 60mg BD HV vs COPD one for each of the intense sampling day (day 1, day 14).
- 4. Boxplot of plasma drug concentration at the follow up visit by cohort.
- 5. Boxplot of Lung CCI15106 concentration by cohort (HV vs COPD).
- 6. Lung CCI15106 concentration by Subject ID.
- 7. Dose proportionality of single and repeat dose and accumulation ratios from Cohorts A and B will be evaluated in Part 1 and Part 2.
- 8. Supportive SAS Output from Statistical Analysis of Loge-transformed Plasma PK Parameters.

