| 4.8. | Systemic PK | PK16a | Individual CCI15106 Plasma Concentration-Time Plot (Linear and Semi-log) (Part 2) | For Cohort B, also overlay profiles on day 1 and day 14 on the same plot (ignore pre-dose PK from day 2 to day 12, and day 15) | SAC | | |
| 4.9. | Systemic PK | Non-Standard PK_F1 | CCI15106 trough Plasma Concentration versus Study Day (Part 1 and Part 2) | Use line plot, All pre-dose from Day 2 following the BD regimens onwards Linear scale only | SAC | | |
| 4.10. | Systemic PK | Non-Standard PK_F1 | CCI15106 Plasma Concentration at follow up visit versus Subject ID (Part 1 and Part 2) | Scatter Plot | SAC | | |
| 4.11. | BAL PK | Non-Standard PK_F2 | Scatter Plot of Lung Drug Concentration versus Subject ID (Part 1 and Part 2) | X Axis: Subject ID Y-Axis: ELF Values | SAC | | |
| 4.12. | BAL PK | Non-Standard PK_F2 | Scatter Plot of Lung Drug Concentration versus Plasma Drug Concentration (BAL cohorts in Part 1 and Part 2) | data for all patients on same page separate colours for healthy and COPD patients Cohorts B for both parts The template is similar to PK_F2, only change the X-axis to plasma drug concentration. | SAC | | |

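### The BAL PK population admits only healthy participants, which contradicts the COPD lung-concentration objective and the healthy-versus-COPD displays that use it

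*SAP*

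**What the plan says.** Section 4 limits BAL PK to "Healthy participants who receive at least one dose of study treatment and who undergo BAL sampling" and who have a post-dose ELF drug result and a urea result. The Systemic PK definition directly above it speaks of participants without that qualifier.

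Section 2.2 gives the secondary objective as "To determine the concentration of CCI15106 in the lung of healthy participants and participants with moderate COPD following repeat dosing of CCI15106-IP". The endpoint is the ELF concentration measured by BAL.

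Section 8.1 assigns BAL PK "for the lung ELF concentration data, unless otherwise specified". No other population is specified for ELF data anywhere in the SAP.

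Section 2.1, which lists departures from the protocol, says that "the BAL PK analysis populations are not defined separately for Part 1 and Part 2".

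On the display side, note 5 to Table 4 in Section 8.1 plans a "Boxplot of Lung CCI15106 concentration by cohort (HV vs COPD"). Section 11.10.7 asks for "separate colours for healthy and COPD patients" in Figure 4.12.

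**The concern.** An analysis population is normally programmed as a flag taken from its written definition, and every display assigned to that population inherits the flag. Here the flag would be set only for healthy participants, while the objective and the displays need COPD participants too.

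A team that follows Section 4 gets ELF outputs with nothing from Part 2. A team that follows the display list must depart from the prespecified population with no documented change. The two instructions cannot both be followed, and the choice would fall to the programming stage, possibly once ELF results are available.

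At stake is the COPD half of the lung-concentration objective. The device-performance objective in Section 2.2 is touched as well: it also covers participants with moderate COPD, and its endpoint includes lung concentrations.

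**Working it through.** The SAP gives no figure to reproduce, so the check sets the relevant sections side by side.

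**1. Who the definition admits.** Section 4 admits healthy participants with BAL sampling and ELF and urea results. Because the neighbouring Systemic PK definition has no such qualifier, the word healthy reads as a real restriction.

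**2. Whether COPD participants have BAL.** They are scheduled to.
- In Section 11.2.1, the schedule that contains the BAL row applies to the repeat-dose cohorts of Parts 1 and 2, except Cohort A of Part 1.
- Section 5.1 identifies Part 2 Cohort B as COPD participants on repeat dosing.
- The screening schedule limits coagulation testing to the BAL cohorts, and coagulation Tables 3.31 and 3.32 are assigned to Cohorts B of Part 1 and Part 2.
- The legend for Figure 4.5 (plasma concentration before BAL) names Cohort B of Part 2 as COPD.

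**3. Whether another population catches COPD ELF data.** None does. Section 8.1 makes BAL PK the default for ELF and no exception follows. Section 2.1 says there is no separate definition by part.

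**4. What each BAL PK display needs, and what it would hold if the definition were applied literally.**

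| Display | What the SAP asks for | COPD participants under the literal definition |
|---|---|---|
| Table 4.3 | ELF summary by cohort | None |
| Figure 4.6 | ELF boxplot by cohort; Table 4 note 5 specifies healthy versus COPD | None |
| Figure 4.11 | ELF by subject, Part 1 and Part 2 | None |
| Figure 4.12 | ELF against plasma, healthy and COPD in different colours, Cohorts B of both parts | None |

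**Count.** Four of the four BAL PK displays would hold no COPD participant. For three of them (Figures 4.6, 4.11 and 4.12) the SAP explicitly calls for COPD or Part 2 data. For Table 4.3 the need is inferred from its by-cohort layout and from the objective.

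**5. What is not affected.** Figure 4.5 and the other plasma displays run on Systemic PK, which admits COPD participants.

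**The case against.** The strongest reply is that this is an obvious leftover. Everything else points to including COPD: the objective, the BAL schedule, Table 4 note 5, and the notes to Figures 4.11 and 4.12. Section 8.1.2.1 also plans ELF summaries for whichever cohorts have ELF data. Section 2.1 declares no exclusion of COPD. The word may have survived from merging separate Part 1 and Part 2 definitions, although that is an inference because the protocol is not at hand. On this view a programmer would notice the clash and include Part 2. The endpoint is also secondary and descriptive, Section 2.4 states that no hypotheses are tested, and no model uses BAL PK.

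Much of this stands. The intended population can be recovered from the rest of the document, and no biased estimate has been shown. But the display notes expose the conflict without resolving it, and the definition is the text that governs who is analysed.

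Two stronger readings are tempting and are not supported.

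- A reader might infer that the plan has decided to exclude COPD lung data. It has not. The exclusion follows only if one word is applied against the rest of the SAP.
- A reader might infer that, because the definition refers to study treatment and Table 4.3 is by cohort, placebo BAL samples would be pooled with active ones. The SAP does not say that placebo BAL samples are assayed, and BAL PK membership requires an ELF drug result. The layout of Table 4.3 is a sponsor standard that is not shown. In the cohort layouts that are shown (shells SAFE_T1 and SAFE_T2), placebo has its own column. Nothing here establishes a placebo problem or a reason to alter the Systemic PK definition.

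**Conclusion.** The point holds as an internal contradiction. The BAL PK definition in Section 4 is wrong as written, because it cannot serve the secondary objective or the displays assigned to it.

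Its size, if applied literally, is all Part 2 ELF results and all four BAL PK displays. In number of participants or samples the size is unknown, because the SAP does not give the count of COPD participants undergoing BAL. The plasma analyses are unaffected.

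The conclusion rests on two readings of the SAP: that the repeat-dose schedule means BAL is performed in Part 2 Cohort B, and that populations are programmed from Section 4. Although the endpoint is descriptive, the correction should be made before the populations are flagged and the data unblinded, because the current text prescribes an ELF analysis with no COPD participants.

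**What to change.** In the BAL PK row of Section 4, replace the opening words with *Participants (healthy or with moderate COPD) who receive*. Leave the remaining criteria unchanged: at least one dose, BAL sampling, post-dose ELF and urea results, and study-team review of samples affected by deviations. No change to the Systemic PK population is needed on this evidence.

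The display list then works as it stands, since it already separates results by cohort or by healthy and COPD status. If the protocol's own definition differs from the corrected wording, record the difference in Section 2.1.

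The cost is one sentence of SAP text, with no additional data, samples or analyses.

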4.1. Protocol Deviations

Important protocol deviations (including deviations related to study inclusion/exclusion criteria, conduct of the trial, patient management or patient assessment) will be summarised and listed.

Protocol deviations will be tracked by the study team throughout the conduct of the study Data will be reviewed prior to unblinding and freezing the database to ensure all important deviations and deviations which may lead to exclusion from the analysis are captured and categorised on the protocol deviations dataset.

 This dataset will be the basis for the summaries and listings of protocol deviations.

5. CONSIDERATIONS FOR DATA ANALYSES AND DATA HANDLING CONVENTIONS

- There are no planned examinations of covariates and subgroups.
- There are no planned adjustments made for multiple centres in this study as this is a single centre study.
- There are no planned adjustments for multiple comparisons or multiplicity.

5.1. Study Treatment & Sub-group Display Descriptors

| | Treatment Group Descriptions | | | | | | | |
|--|-------------------------------------|----------------------------|---|-----------|--|--|--|--|
| RandAll NG Data Displays for Reporting | | | | | | | | |
| Code | Description | Display Header | Footnote Treatment Description | Order [1] | | | | |
| S1 | CCI15106-IP 60 mg – Single Dose | CCI15106 SD 60mg(HV) | CCI15106-IP 60 mg Single Dose for Part 1, Cohort A | 1 | | | | |
| S2 | CCI15106-IP 120 mg – Single Dose | CCI15106 SD 120mg(HV) | CCI15106-IP 120 mg Single Dose for Part 1, Cohort A | 2 | | | | |
| R1 | CCI15106-IP 30 mg - BID | CCI15106 BID 30mg(HV) | CCI15106-IP 30 mg BID for Part 1, Cohort A | 3 | | | | |
| R2 | CCI15106-IP 60 mg - BID | CCI15106 BID 60mg(HV) | CCI15106-IP 60 mg BID For Part 1, Cohort B | 4 | | | | |
| Р | Placebo | Placebo(HV) | Placebo for Part 1 Cohorts A and B | 5 | | | | |
| S1 | CCI15106-IP 60 mg – Single Dose | CCI15106 SD 60mg(COPD) | CCI15106-IP 60 mg Single Dose for Part 2, Cohort A COPD | 6 | | | | |
| R2 | CCI15106-IP 60 mg - BID | CCI15106 BID 60mg(COPD) | CCI15106-IP 60 mg BID for Part 2, Cohort B COPD | 7 | | | | |
| Р | Placebo | Placebo(COPD) | Placebo for Single Dose and BID for COPD | 8 | | | | |
| BYS | Bystander Cohort | Bystander | Bystander | 9 | | | | |

NOTES:

1. Order represents treatments being presented in TFL, as appropriate.

5.2. Baseline Definitions

5.2.1. Baseline Definitions

For all endpoints (except as noted in baseline definitions) the baseline value will be the latest pre-dose assessment.

For tabulated safety summaries, only the scheduled assessments will be included in the summary tables.

| Parameter | Study Assessn | Study Assessments Considered as Baseline | | | | | | | | | |
|----------------------------------|---------------|--|----------------------|------------------|--|--|--|--|--|--|--|
| | Screening | Day -1 | Day 1 (Pre- Dose) | in Data Display | | | | | | | |
| Safety | | | | | | | | | | | |
| 12 Lead ECG & Vital Signs | Х | - | Х | Day 1 (Pre-Dose) | | | | | | | |
| Spirometry | Х | - | X | Day 1 (Pre-Dose) | | | | | | | |
| Haematology/Chemistry/Urinalysis | Х | X | - | Day - 1 | | | | | | | |
| Telemetry | - | - | X | Day 1 (Pre-Dose) | | | | | | | |

NOTES:

 Unless otherwise stated, the mean of replicate assessments at any given time point will be used as the value for that time point.

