5.2.2. Derivations and Handling of Missing Baseline Data

| Definition | Reporting Details |
|------------------------|---|
| Change from Baseline | = Post-Dose Visit Value – Baseline |
| % Change from Baseline | = 100 x [(Post-Dose Visit Value – Baseline) / Baseline] |

NOTES:

- Unless otherwise specified, the baseline definitions specified in Section 5.2.1 will be used for derivations for endpoints / parameters and indicated on summaries and listings.
- Unless otherwise stated, if baseline data are missing no derivation will be performed and will be set to missing.
- The baseline definition will be footnoted on change from baseline displays wherever applicable.

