Repeat dose schedule to be followed for repeat dose cohorts in Parts 1 and 2 (other than Cohort A Part 1)

| Procedure | | | | | | | Trea | tment P | eriod, [| Days | | | | | | |
|---|----------------|------------|---|----|---|---|------|---------|----------|------|-----|----|-----|----------------|----|-----------------|
| | -1 | 1 | 2 | 3 | 4 | 5 | 6 | 7 | 8 | 9 | 10 | 11 | 12 | 13 | 14 | 15 |
| Inclusion and exclusion criteria | X | | | | | | | | | | | | | | | |
| Brief physical examination, oral examination | X | | | | | | | | | | | | | | | X |
| Substance testing (drugs, alcohol, tobacco1) | X | | | | | | | | | | | | | | | |
| Inhaler device training ² | X | | | | | | | | | | | | | | | |
| Serum pregnancy test in women | X | | | | | | | | | | | | | | | |
| Admittance to clinic | X | | | | | | | | | | | | | | ĺ | |
| Randomization | X ₃ | | | | | | | | | | | | | | 1 | |
| Discharge | | | | | | | | | | | | | | | ĺ | X4 |
| Dosing procedure training with bystanders | | X5 | | | | | | | | | | | | | 1 | |
| Haematology, clinical chem and urinalysis (include liver chem)6 | Х | | | | | | | Х | | | | | | | | Х |
| Spirometry | | X 7 | | Χ8 | | | χ8 | | | | | Χ8 | | | Х7 | |
| Telemetry (starting 30 min pre-morning dose and continuous at least 4h post-morning dose) | | Х | | | | | | Х | | | | | | X ⁹ | | |
| 12-lead ECG and vital signs ¹⁰ | XXX | Χ | | Χ | Χ | | Х | Х | Χ | | X11 | | X11 | | ĺ | |
| CCI15106-IP or placebo treatment BID, device incident assessment BID ¹² | | Х | Х | Х | Х | Х | Х | Х | Х | Х | Х | Х | Х | Х | Х | |
| PK blood sample ¹³ | | Χ | Х | | Χ | | Х | | Χ | | Х | | Х | | Х | X |
| BAL | | | | | | | | | | | X14 | | | | | |
| Urea blood sample | χ15 | | | | | | | | | | | | | | | |
| AE review | () | | | | | | | | | | | | | | | |
| SAE review | | | | | | | | | | | | | | | | |
| Concomitant medication review | (| | | | | | | | | | | | | | | > |

- 1. Tobacco test to be performed only in healthy participants
- 2. Day -1 inhaler training may be done on Day 1 instead, before the first dose administration. Other time-points may be added per investigators discretion.
- 3. Can be performed on Day 1 prior to dosing
- 4. After all procedures and assessments are complete
- 5. To be done only in Cohort(s) where bystanders are present. Can be performed on Day -1 instead, if desired. Other time-points may be added per investigators discretion.
- 6. To be drawn fasting (for at least 8 h)

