- 7. To be performed at the following timepoints in the mornings only: pre-dose, and 0.25 (in participants with COPD only), 0.5, 1, 4 h post-dose
- 8. To be performed at the following timepoints in the mornings only: pre-dose and 4 h post-dose

- 9. Telemetry may be performed on Days 11 or 12 instead, not to coincide with the BAL procedure.
- 10. ECG and vital signs to be obtained 2 h after the morning dose
- 11. When BAL is performed, vital signs and ECG will be performed before and after the procedure and oxygen saturation will be measured continuously.
- 12. For cohort with bystanders, BID doses may have ±1.5 h window.
- 13. PK samples on days 1 and 14 will be collected at the following timepoints: pre-dose, 0.25, 0.5, 0.75, 1, 2, 4, 6, 8, 10, 12 h. The evening dose will be given after 12 h post-dose sample is collected. On all other days, PK sample will be collected once, before the morning dose. When BAL is performed, one additional PK sample will be collected after dosing immediately prior to bronchoscopy
- 14. Done once during these four days, as soon as possible (within 1 h) after the first dose of the day
- 15. To be collected immediately before bronchoscopy

Schedule for Cohort C Part 1 (bystanders and air monitoring), to be executed concomitantly with Cohort B Part 1

| Procedure Treatment Period, Days | | | | | | | | | | | | | | | | |
|---|----------------|----------------|---|-----------------------|----|--------------------|-------------------|----------------|----|---|-----------------------|----|----|----|----------------|----|
| | -1 | 1 | 2 | 3 | 4 | 5 | 6 | 7 | 8 | 9 | 10 | 11 | 12 | 13 | 14 | 15 |
| Inclusion and exclusion criteria | X | | | | | | | | | | | | | | | |
| Brief physical examination, oral examination | X | | | | | | | | | | | | | | | Х |
| Substance testing (drugs, alcohol, tobacco) | Х | | | | | | | | | | | | | |] | |
| Serum pregnancy test in women | Х | | | | | | | | | | | | | | | |
| Admittance to clinic | X | | | | | | | | | | | | | | | |
| Discharge | | | | | | | | | | | | | | | | X1 |
| Training ² | X | | | | | | | | | | | | | | | |
| Haematology, clinical chem and urinalysis (include liver chem)3 | X | | | | | | | Χ | | | | | | | | Χ |
| Exposure to dosing | | Χ | Χ | X | Χ | X | X | X | Χ | X | Χ | X | X | X | Χ | |
| PK blood sample | | X ⁴ | | | | | | X ⁴ | | | | | | | X ⁴ | X |
| Stationary pump air monitoring ⁵ | | Χ | | | | | | Χ | | | | | | | Χ | |

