| Personal exposure pump monitoring ⁶ | | Χ | | | | | | Χ | | | | | | | Χ | |
| 12-lead ECG and vital signs | XXX | X7 | | X ⁷ | χ7 | | χ7 | X7 | X7 | | X ⁷ | | X7 | | | |
| AE review | ←) | | | | | | | | | | | | | | | |
| SAE review | ← | | | | | = -> | | | | | | | | | | |
| Concomitant medication review | (| | | | | | = > | | | | | | | | | |

- 1. After all procedures and assessments are complete
- 2. Day -1 training may be done on Day 1 instead, before the first dose administration. Other time-points may be added per investigators discretion
- 3. To be drawn fasting (for at least 8 h)
- 4. PK samples will be collected pre-dose and 15 min after the dosing participant takes their first daily dose. In addition, on days 7 and 14, one sample on each day will be collected before the dosing participant takes the first daily dose. On day 15, one sample will be collected before discharge.
- 5. Samples of air to be collected for 20 and 60 min during and after the first morning dose
- 6. Samples of air to be collected for 15 min during and after the first morning dose
- 7. ECG and vital signs to be obtained 2 h after the exposure to morning dose

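### The ECG and vital-sign baseline row excludes Day -1, the only pre-treatment reading scheduled after screening in Cohort B (Parts 1 and 2) and Cohort C

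*SAP*

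**What the plan says.** SAP Section 5.2.1 opens with a general rule: "For all endpoints (except as noted in baseline definitions) the baseline value will be the latest pre-dose assessment". The table beneath it then lists, by parameter, which assessments count. In the row "12 Lead ECG & Vital Signs", Screening and Day 1 pre-dose are marked, Day -1 carries a dash, and the display baseline is Day 1 pre-dose. A note adds that replicates at a time point are averaged.

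Section 5.2.2 applies these definitions to all derivations and states that "if baseline data are missing no derivation will be performed and will be set to missing".

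Section 11.2.1 sets out when the readings are taken:

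- **Cohort B, Parts 1 and 2.** These follow the schedule headed "Repeat dose schedule to be followed for repeat dose cohorts in Parts 1 and 2 (other than Cohort A Part 1"). Its ECG and vital-sign row shows three marks on Day -1 and a single mark on Day 1. The footnote on that row reads "ECG and vital signs to be obtained 2 h after the morning dose".
- **Cohort C (bystanders).** The row begins "12-lead ECG and vital signs | XXX", with the three marks under Day -1. The Day 1 mark is footnoted "ECG and vital signs to be obtained 2 h after the exposure to morning dose".
- **Cohort A, Part 2.** The single-dose schedule has three marks at Day 1 pre-dose. Cohort A of Part 1 uses the same schedule on its single-dose days, Day 1 among them.

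**The concern.** The row names a baseline that three of the five cohorts are not scheduled to have, and excludes the reading taken in its place.

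ECG and vital signs are part of the primary safety endpoint (Section 2.2). The affected columns are 60 mg BID in healthy participants, 60 mg BID in COPD (the only repeat-dose COPD group), the bystanders, and the Cohort B members of the two pooled placebo groups. Each placebo group would combine Cohort A members who have the stated baseline with Cohort B members who do not.

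Two programmers following the same SAP could therefore produce different change-from-baseline tables, and one of them could leave these cohorts empty.

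**Working it through.** There is no arithmetic to reproduce; the check sets the baseline row against each cohort's schedule.

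**Step 1. Which cohorts have the named baseline?**

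| Cohort | Pre-treatment ECG and vital signs after screening | First Day 1 reading in relation to dose or exposure | Day 1 pre-dose baseline scheduled? |
|---|---|---|---|
| Part 1 Cohort A | Day -1, and Day 1 pre-dose by reference to the single-dose schedule | before | yes |
| Part 1 Cohort B | Day -1 | 2 h after | no |
| Part 1 Cohort C | Day -1 | 2 h after | no |
| Part 2 Cohort A | Day 1 pre-dose | before | yes |
| Part 2 Cohort B | Day -1 | 2 h after | no |

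Two cohorts have it and three do not.

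**Step 2. Do the other rows of the baseline table have the same problem?** No. Spirometry has a Day 1 pre-dose measurement in every dosed cohort. Telemetry starts 30 minutes before the morning dose. Laboratory tests are taken on Day -1 and their row uses Day -1. The mismatch is confined to the ECG and vital-sign row, and the laboratory row shows that the table can carry a Day -1 baseline.

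**Step 3. What does the SAP yield for Cohorts B and C?** Three readings can be defended:

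1. Only the display baseline counts. Day 1 pre-dose does not exist, so Section 5.2.2 sets every change to missing.
2. The marked columns are candidates in order of recency. Screening is the only one left. The screening schedule allows it up to 30 days before Day 1 in Part 1 and up to 45 days in Part 2, and it carries a single mark.
3. The general rule overrides the table. Day -1 is then the latest pre-dose assessment and is used.

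The first two follow the table and discard the Day -1 replicates. The third requires setting the table aside, although the general rule yields to exceptions noted in the baseline definitions.

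**Step 4. Which outputs depend on it?** Three groups of three tables, so 3 × 3 = 9:

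- change in ECG values: 3.40-3.42
- worst change in QTcB and QTcF by PCI category: 3.46-3.48
- change in vital signs: 3.52-3.54

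The change criteria in Section 11.7.2 (QTc increase above 30 msec, and 60 msec or more) and Section 11.7.3 (systolic and diastolic pressure, heart rate) also need this baseline.

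**Step 5. Do the mock shells settle the matter?** No. SAFE_T7 labels the pre-treatment row as baseline for the PR interval but as screening for QRS and QTcB.

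**The case against.** The best defence is the general rule. Read alone, it picks Day -1 for Cohorts B and C, which is the sensible baseline, and a careful programmer might do exactly that. This stands in part: Day -1 is a possible outcome, so the results are not certain to be lost. It does not clear the plan, because the rule gives way to the table and the table excludes Day -1 for this row.

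It is also fair that no hypothesis is tested (Section 2.4), that these displays are descriptive, and that the individual ECG and vital-sign values are listed, so the changes could be recomputed. That limits the harm. It does not make the stated rule right.

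A reader might infer more than the documents support:

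- **That every repeat-dose group is affected, or the longest-dosed one.** Part 1 Cohort A also receives BID dosing and has the stated baseline. It is dosed on Days 1, 3 and 6-19, so 2 + 14 = 16 days, against 14 days (Days 1-14) in Cohort B.
- **That all change values must be missing.** Screening is marked as acceptable and is scheduled for all cohorts, so missing is one reading, not the only one.
- **That the 2 h post-dose value would serve as baseline.** Both the general rule and the column label say pre-dose.
- **That all PCI results are affected.** Laboratory change flags use the Day -1 laboratory baseline. Absolute QTc categories (3.43-3.45) and absolute vital signs (3.49-3.51) need no subtraction of baseline.
- **That the participant numbers in the mock shells measure the impact.** They differ from shell to shell and are placeholders.

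**Conclusion.** Wrong as written. The ECG and vital-sign row of Section 5.2.1 contradicts the schedules for Cohort B of Parts 1 and 2 and for Cohort C, which is 3 of 5 cohorts. For these cohorts, and for the Cohort B members of pooled placebo, the SAP does not determine change from baseline in nine planned tables or in the change-based ECG and vital-sign PCI criteria. Following the table gives a missing result or a screening baseline up to 30 or 45 days before Day 1; Day -1 is reached only by letting the general rule override the table.

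The 30 and 45 days are the limits of the screening window; actual gaps may be shorter. The three marks on Day -1 are taken to mean replicates, since no schedule footnote defines them. The contradiction does not depend on that, because a Day -1 assessment is scheduled either way.

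**What to change.** In Section 5.2.1, change the ECG and vital-sign row as follows:

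- mark Day -1 as an accepted assessment;
- define baseline as the mean of the Day 1 pre-dose replicates for Cohorts A (Parts 1 and 2), and as the mean of the Day -1 replicates for Cohorts B (Parts 1 and 2) and Cohort C;
- carry the same wording into the display column.

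Footnote the cohort-specific definition on Tables 3.40-3.42, 3.46-3.48 and 3.52-3.54, as Section 5.2.2 already requires for change displays. Make the pre-treatment row label in SAFE_T7 consistent across parameters.

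The cost is one table row, a footnote and a shell correction. No new assessment is needed, because the Day -1 readings are already scheduled. The edit should be made before unblinding.
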